#### 10.3 Methods for Evaluation of Measurable Disease

All measurements should be taken and recorded in metric notation using a ruler or calipers.

The same method of assessment and the same technique should be used to characterize each identified and reported lesion at baseline and during follow-up. Imaging-based evaluation is preferred to evaluation by clinical examination unless the lesion(s) being followed cannot be imaged but are assessable by clinical exam. A collection of scans (but not independent review) is mandatory per study protocol and confirmation of progression is required.

#### **10.3.1** Clinical Lesions

Clinical lesions will only be considered measurable when they are superficial (e.g., skin nodules and palpable lymph nodes) and  $\geq 10$  mm diameter as assessed using calipers (e.g., skin nodules). In the case of skin lesions, documentation by color photography, including a ruler to estimate the size of the lesion, is recommended.

#### **10.3.2** Chest X-Ray

Lesions on chest x-ray are acceptable as measurable lesions when they are clearly defined and surrounded by aerated lung; however, CT is preferable.

#### 10.3.3 Conventional CT and MRI

This guideline has defined measurability of lesions on CT scan based on the assumption that CT slice thickness is 5 mm or less. If CT scans have slice thickness greater than 5 mm, the minimum size for a measurable lesion should be twice the slice thickness. MRI is also acceptable in certain situations (e.g. for body scans). Ideally, the same type of scanner should be used, and the image acquisition protocol should be followed as closely as possible to prior scans.

#### 10.3.4 PET-CT

At present, the low dose or attenuation correction CT portion of a combined PET-CT is not always of optimal diagnostic CT quality for use with RECIST measurements. However, if the site can document that the CT performed as part of a PET-CT is of identical diagnostic quality to a diagnostic CT (with IV and oral contrast), then the CT portion of the PET-CT can be used for RECIST measurements and can be used interchangeably with conventional CT in accurately measuring cancer lesions over time. Note, however, that the PET portion of the CT introduces additional data which may bias an investigator if it is not routinely or serially performed.

#### 10.3.5 Tumour Markers

Tumour markers alone cannot be used to assess response. If markers are initially above the upper normal limit, they must normalize for a patient to be considered in complete clinical response.

#### 10.3.6 Cytology, Histology

These techniques can be used to differentiate between partial responses ([i]PR) and complete responses ([i]CR) in rare cases (e.g., residual lesions in tumour types, such as germ cell tumours, where known residual benign tumours can remain).

Cytology should be obtained if an effusion appears or worsens during treatment when the measurable tumour has met criteria for response or stable disease.

#### **10.3.7 FDG-PET**

While FDG-PET response assessments need additional study, it is sometimes reasonable to incorporate the use of FDG-PET scanning to complement CT scanning in assessment of progression (particularly possible 'new' disease). New lesions on the basis of FDG-PET imaging can be identified according to the following algorithm:

- A. Negative FDG-PET at baseline, with a positive FDG-PET at follow-up is a sign of PD based on a new lesion.
- B. No FDG-PET at baseline and a positive FDG-PET at follow-up: If the positive FDG-PET at follow-up corresponds to a new site of disease confirmed by CT, this is PD. If the positive FDG-PET at follow-up is not confirmed as a new site of disease on CT, additional follow-up CT scans are needed to determine if there is truly progression occurring at that site (if so, the date of PD will be the date of the initial abnormal FDG-PET scan). If the positive FDG-PET at follow-up corresponds to a pre-existing site of disease on CT that is not progressing on the basis of the anatomic images, this is not PD.

**Note:** A 'positive' FDG-PET scan lesion means one that is FDG avid with an uptake greater than twice that of the surrounding tissue on the attenuation corrected image.

## 10.4 Response Criteria for Patients with Solid Tumour and Measurable Disease

## 10.4.1 Time Point and Best Overall Response

The time point response is calculated using the response assigned for each category of lesion (as for RECIST 1.1), but takes into account the last time point response. The algorithm for patients with no previous iUPD is identical to RECIST 1.1 (Eisenhaur, 2009). For patients with iUPD at the last time point response, the next time point response is dependent on the status of all lesions, including target, non-target, new lesion target, and new lesion non-target; on whether any increase in size has occurred (either a further increase in size or a sufficient increase to assign a new iUPD if the criteria were not previously met); or the appearance of additional new lesions.

For iRECIST, the best overall response (iBOR) is the best time point response recorded from the start of the study treatment until the end of treatment, considering any requirement for confirmation. iUPD will not override a subsequent best overall response of iSD, iPR, or iCR, meaning that iPR or iSD can be assigned (time point response or iBOR) even if new lesions have not regressed, or if unequivocal progression (non-target lesions) remains unchanged, providing that the criteria for iCPD are not met. The duration of iCR and iPR is from the time point when the criteria for iCR or iPR are first met, whereas the duration of iSD is still calculated from baseline.

Assessments that are not done or are not evaluable should be disregarded. For example, an iUPD followed by an assessment that was not done or not evaluable, and then another unconfirmed progressive disease, would be indicative of iCPD.

Assessments done after protocol therapyis discontinued can be considered in identification of iBOR. All imaging done during the follow-up period should continue to be recorded on the case report form ad used to assess response until subsequent therapies are initiated, as the protocol and informed consent document permit.

## **10.4.2** Evaluation of Target Lesions

Complete Response (CR): Disappearance of all target and non-target lesions. Any pathological lymph nodes (whether target or non-target) must have reduction in short axis to <10 mm. If immunocytology is available, no disease must be detected by that methodology. Normalization of urinary catecholamines or other tumour markers if elevated at study enrollment (for patients with neuroblastoma).

**Partial Response (PR):** At least a 30% decrease in the sum of the diameters of target lesions, taking as reference the baseline sum diameters

Unconfirmed progressive disease (iUPD): At least a 20% increase in the sum of the diameters of target lesions, taking as reference the smallest sum on study (this includes the baseline sum if that is the smallest on study). In addition to the relative increase of 20%, the sum must also demonstrate an absolute increase of at least 5 mm. iUPD must be assessed between four to eight weeks to confirm progression and become iCPD.

Confirmed progressive disease (iCPD): iUPD must be assessed between four to eight weeks to confirm progression and be deemed as iCPD. There must be at least a 20% increase in the sum of the diameters of target lesions, taking as reference the smallest sum on study (this includes the baseline sum if that is the smallest on study). In addition to the relative increase of 20%, the sum must also demonstrate an absolute increase of at least 5 mm.

**Progressive Disease (PD):** New Lesion if the next imaging assessment, conducted at least four (4) weeks, but not more than eight (8) weeks after iUPD confirms further progression from iUPD with either an increase of at least 5 mm in the absolute value of the sum of NLT or an increase (but not necessarily unequivocal increase) in the size of NLNT lesions OR the appearance of additional new lesions.

**Note:** In presence of SD or PR in target disease but unequivocal progression in non-target or non-measurable disease, the patient has PD if there is an overall level of substantial worsening in non-target disease such that the overall tumour burden has increased sufficiently to merit discontinuation of therapy.

**Stable Disease (SD):** Neither sufficient shrinkage to qualify for PR nor sufficient increase to qualify for iUPD or PD, taking as reference the smallest sum diameters while on study.

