## 3.2 Part II - Treatment and Companion Biomarker Study Duration

Nivolumab will be given in four (4) week cycles (one cycle equals two (2) drug administrations, two (2) weeks apart) for a maximum of up to two (2) years if clinical and radiological benefit is evident. After completion of treatment, patients will enter standard follow up for twelve (12) months. Patients with confirmed disease progression or excessive toxicity will discontinue treatment.

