For target lesions, iCR, iPR, and iSD can all be assigned after iUPD has been documented, as long as iCPD was not confirmed. iUPD is defined by RECIST 1.1 criteria for progressive disease and can be assigned multiple times as long as iCPD is not confirmed at the next assessment. Progression is confirmed in the target lesion category if the next imaging assessment after iUPD (4–8 weeks later) confirms a further increase in sum of measures of target disease from iUPD, with an increase of at least 5 mm. However, the criteria for iCPD (after iUPD) are not considered to have been met if CR, PR or SD criteria (compared with baseline and as defined by RECIST 1.1) are met at the next assessment after iUPD (Seymour, 2017). The status is reset (unlike RECIST 1.1, in which any progression precludes later complete response, partial response, or stable disease). iCR, iPR, or iSD should then be assigned; and if no change is detected, then the time point response is iUPD (Seymour, 2017).

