If iUPD is not confirmed at the next assessment, then the appropriate response will be assigned (iUPD if the criteria are still met, but no worsening, or iSD, iPR or iCR if those criteria are met compared to baseline). The prior documentation of iUPD does not preclude assigning iCR, iPR, or iSD in subsequent time-point assessments or as best overall response (BOR) providing that iCPD is not documented at the next assessment after iUPD. Tumour disease evaluation will be by objective response rate (ORR = complete response [CR] and partial response [PR]). Patients with response of 'stable disease' (SD), iCR, iPR, or iSD will also be reported as part of the final analysis of clinical benefit, but will not contribute to the primary efficacy outcome measure (Seymour, 2017).

Treatment beyond initial iUPD is permitted in patients who are clinically stable to continue on treatment until the next assessment (≥four [4] weeks later); this next imaging assessment should

be no longer than eight (8) weeks later, to ensure that patients remain fit for salvage therapies All decisions regarding continuation or discontinuation of therapy should be made by the patient, the local PI and either the Study Chair or Co-Chair. An assignment of clinical stability requires that no worsening of performance status has occurred, that no clinically relevant increases in disease-related symptoms such as pain or dyspnoea occur that are thought to be associated with disease progression, and that no requirement for intensified management of disease-related symptoms exists, including increased analgesia, radiotherapy, or other palliative care.

Patients who have iUPD and are not clinically stable should be designated as not clinically stable in the case report form. This designation will allow the best overall response to be calculated and the date of iUPD to be used in estimates of PFS.

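### For iRECIST target lesions the protocol defines confirmed progression in two incompatible ways, so a plateau after first progression is confirmed in Section 10.4.2 and unconfirmed in Sections 10.2.3 and 10.2.7

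*Protocol*

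**What the plan says.** All references are to the Protocol.

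- **Section 10.4.2, iUPD:** "At least a 20% increase in the sum of the diameters of target lesions, taking as reference the smallest sum on study", together with an absolute increase of at least 5 mm.
- **Section 10.4.2, iCPD:** after a reassessment at four to eight weeks, "There must be at least a 20% increase in the sum of the diameters of target lesions, taking as reference the smallest sum". It adds: "In addition to the relative increase of 20%, the sum must also demonstrate an absolute increase of at least 5 mm". Growth beyond the iUPD scan is not mentioned.
- **Section 10.2.3:** target-lesion progression is confirmed if the next scan "confirms a further increase in sum of measures of target disease from iUPD, with an increase of at least 5 mm". If there is no change, the time point is iUPD again.
- **Section 10.2.7:** confirmation needs a further increase over the last assessment. Otherwise the time point is "iUPD if the criteria are still met, but no worsening", or iSD, iPR or iCR if those criteria are met against baseline.
- **Section 10.4.1:** assessments that were missed or not evaluable are disregarded, with the example that "an iUPD followed by an assessment that was not done or not evaluable, and then another unconfirmed progressive disease, would be indicative of iCPD".
- **Consequences:** Sections 10.2.3 and 10.2.7 allow a response after iUPD only if iCPD was not documented. Section 3.2 states: "Patients with confirmed disease progression or excessive toxicity will discontinue treatment".

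**The concern.** The two rules use different reference scans. Section 10.4.2 measures from the smallest sum, and Sections 10.2.3 and 10.2.7 measure from the iUPD scan. A tumour that grows, holds steady and later shrinks gets one status from the first and another from the second. Section 10.2 names this reset after apparent progression as the main change from RECIST 1.1, so the conflict falls on the pattern for which iRECIST was adopted.

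Three things depend on the status: whether a later shrinkage can be assigned as iPR or iCR, whether a confirmed progression is recorded for PFS, and whether the treatment rule in Section 3.2 is triggered. Sites act on iCPD while the patient is on study, so a later analysis document could not fully undo an inconsistent assignment.

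**Working it through.** **Inputs.** The rules are those of Sections 10.4.2, 10.2.3 and 10.2.7. The decision rules come from Section 11. Cohort A stops at 1 or fewer responses in 10, rejects at 5 or more in 20, and is designed for a 35% response rate. Cohort B stops at 1 or fewer in 10, rejects at 6 or more in 30, and is designed for 30%. The lesion sums below are assumed for illustration.

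**1. Both rules on one patient.** Let N be the smallest sum, U the sum at iUPD and S the next sum.

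- Section 10.4.2: iCPD if S ≥ 1.2N and S − N ≥ 5 mm.
- Sections 10.2.3 and 10.2.7: iCPD on target lesions if S − U ≥ 5 mm.

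Take baseline = N = 50 mm and U = 62 mm. The increase is 12/50 = 24% and 12 mm, so this scan is iUPD. Under 10.4.2 the threshold is 1.2 × 50 = 60 mm. Under 10.2.3 it is 62 + 5 = 67 mm.

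| Next sum S | Section 10.4.2 | Sections 10.2.3 and 10.2.7 |
|---|---|---|
| 59 mm (+18% on N) | not iCPD | not iCPD |
| 60 mm (+20%) | iCPD | not iCPD |
| 62 mm (+24%, no change from U) | iCPD | iUPD |
| 66 mm (+32%, 4 mm above U) | iCPD | not iCPD |
| 67 mm (+34%, 5 mm above U) | iCPD | iCPD |

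In whole millimetres the rules disagree from 60 to 66 mm, which covers slight shrinkage, a plateau and growth under 5 mm. The disagreement runs one way. Since U ≥ 1.2N, any S ≥ U + 5 also meets the 10.4.2 test, so 10.4.2 confirms every case that 10.2.3 confirms on target lesions, and more.

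**2. A later response.** Suppose the sums run 50, 62, 62, 33 mm. The last is (50 − 33)/50 = 34% below baseline and passes the 30% threshold for PR. Under 10.2.3 and 10.2.7 it can be iPR. Under 10.4.2 iCPD was already documented at the third scan, so it cannot.

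**3. The plan's own power.** Power is the sum, over stage 1 counts x from 2 to 10, of P(x of 10) × P(at least r − x of the remaining n − 10).

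- Cohort A: 0.843 at 35% (stated 85%).
- Cohort B: 0.815 at 30% (stated 80%).

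Both agree with the stated power to within two points.

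**4. Sensitivity to single patients.** These are the chances, at the design response rates, of landing exactly on a deciding count:

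| Count | Cohort A | Cohort B |
|---|---|---|
| 2 of 10 at stage 1 | 17.6% | 23.3% |
| 5 of 20 (A) or 6 of 30 (B), single-stage binomial | 12.7% | 8.3% |
| Same, also passing stage 1 | 10.8% | 5.6% |

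**5. Assumed range of loss.** If a share f of true responders were reclassified, the response rate becomes p(1 − f):

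| f (assumed) | Power, A | Power, B |
|---|---|---|
| 0 | 0.843 | 0.815 |
| 5% | 0.805 | 0.777 |
| 10% | 0.760 | 0.734 |
| 20% | 0.650 | 0.628 |

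The protocol gives no value for f. The table also treats every responder as assessed under iRECIST and every iPR as counted in ORR.

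**The case against.** The best defence reads Section 10.4.2 as one condition among several. Section 10.2.3 says that the response and progression definitions are set out across Section 10.2, Section 10.2.7 is the part headed as confirming progression, and Section 10.4.1 makes the time point after iUPD depend on whether size has increased. On that reading 10.4.2 is a loosely worded outlier. It is an outlier, but the defence does not remove the conflict. The paragraph is written as the definition of iCPD and names its own reference sum, and the new-lesion paragraph that follows it does ask for further progression from iUPD. An assessor using the section on measurable disease would have no reason to add a growth test.

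Other objections stand and limit the point:

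- **Missed scans.** A reader might take the example in Section 10.4.1 as a third definition that needs no growth. The text does not say so. It is only silent on whether a further increase is needed.
- **Treatment and later scans.** A reader might infer that a plateau under 10.4.2 always ends treatment and makes later shrinkage unassessable. Section 10.2.6 lets some patients with increases between 20% and 40% remain on study for up to 12 weeks, and 10.4.1 lets scans after discontinuation count toward best response until another therapy starts. Equally, Section 13.2 lists progression after 12 weeks as a withdrawal criterion without mentioning confirmation, so staying on treatment is not assured under the other rule.
- **Scope.** CNS tumours, lymphoma and leukaemia use other criteria. Sections 10.6.2 and 10.6.3 say that the iUPD terms do not apply to the neuroblastoma efficacy endpoint.
- **Counting toward ORR.** The synopsis defines ORR as CR plus PR under iRECIST, whereas Section 10.2.7 says iCR and iPR do not contribute to the primary outcome. That is a separate conflict. It makes the effect on the primary count uncertain but does not settle which iCPD definition applies.

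**Conclusion.** The contradiction holds for solid tumours with measurable target lesions under iRECIST. The same scan can be confirmed progression in one section and unconfirmed in another, and this affects later response assignment, the PFS record and the application of Section 3.2. In the illustrative case the zone of disagreement is 60 to 66 mm.

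The effect on the trial's conclusions cannot be sized from the protocol. The 10.8% and 5.6% are chances of landing on a deciding count, not chances of a changed decision. A reader might infer that a cohort decision is likely to flip, but that would need the rate of plateau followed by response, which is not given. The power losses in the working rest wholly on assumed shares. What can be said is the direction: applying 10.4.2 can only give the same number of responses as 10.2.3 and 10.2.7, or fewer, and single patients decide at 2 of 10, 5 of 20 and 6 of 30.

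Nor do the documents establish which rule should stand. Because iCPD bears on stopping treatment, that choice belongs to the sponsor.

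**What to change.** The sponsor should state one definition of target-lesion iCPD and use it everywhere:

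1. Reconcile the iCPD paragraph of Section 10.4.2 with Sections 10.2.3 and 10.2.7, naming the reference scan and saying what status an unchanged sum receives.
2. Say in Section 10.4.1 whether a second iUPD after a missed or non-evaluable scan must also meet the further-increase test.
3. Check the agreed definition against the 12-week provisions in Sections 10.2.6 and 13.2.
4. State that the same definition is used by sites, by central review and in the ORR and PFS analyses.

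The cost is wording: two paragraphs in Section 10 and a consistency check of two other sections. No extra scans are needed.

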## 10.4.3 Evaluation of Non-Target Lesions

**Complete Response (CR):** Disappearance of all non-target lesions and normalization of tumour marker level. All lymph nodes must be non-pathological in size (<10 mm short axis).

**Note:** If tumour markers are initially above the upper normal limit, they must normalize for a patient to be considered in complete clinical response.

**Non-CR/Non-PD:** Persistence of one or more non-target lesion(s) and/or maintenance of tumour marker level above the normal limits.

**Progressive Disease (PD):** Appearance of one or more new lesions and/or unequivocal progression of existing non-target lesions. Unequivocal progression should not normally trump target lesion status. It must be representative of overall disease status change, not a single lesion increase.

**Best Overall Response (iBOR):** Each patient will be classified according to his "best response" for the purposes of analysis of treatment effect. Best response is determined as outlined in *Section* 10.4.1 and 11 from a sequence of overall response assessments.

### 10.5 Response Criteria for Patients with Solid Tumours and Evaluable Disease

**Evaluable Disease:** The presence of at least one lesion, with no lesion that can be accurately measured in at least one dimension. Such lesions may be evaluable by nuclear medicine techniques, immunocytochemistry techniques, tumour markers or other reliable measures.

**Complete Response (CR):** Disappearance of all evaluable disease.

Partial Response (PR): Partial responses cannot be determined in patients with evaluable disease

**Stable Disease (SD):** That which does not qualify as Complete Response (CR), Partial Response (PR), or Progressive Disease.

**Unconfirmed progressive disease (iUPD):** The appearance of one or more new lesions or evidence of laboratory, clinical, or radiographic progression. iUPD must be assessed between four to eight weeks to confirm progression and become iCPD.

**Confirmed progressive disease (iCPD):** iUPD must be assessed between four to eight weeks to confirm progression and be deemed as iCPD.

**Progressive Disease (PD):** The appearance of one or more new lesions or evidence of laboratory, clinical, or radiographic progression if the next imaging assessment, conducted at least four (4) weeks, but not more than eight (8) weeks after iUPD confirms further progression from iUPD with either an increase of at least 5 mm in the absolute value of the sum of NLT or an increase (but not necessarily unequivocal increase) in the size of NLNT lesions OR the appearance of additional new lesions.

**Best Overall Response (iBOR):** Each patient will be classified according to his "best response" for the purposes of analysis of treatment effect. Best response is determined as outlined in *Section* 10.4.1 and 11 from a sequence of overall response assessments.

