## 10.2.5 Assessment of New Malignant Lesions

The assessment of non-target lesions at each time point follows similar principles. iUPD (but not iCPD) can have been documented before iCR or when the criteria for neither CR nor PD have been met (referred to as non-iCPD/non-iUPD) and can be assigned several times, as long as iCPD was not confirmed. iUPD is defined by RECIST 1.1 criteria; however, iUPD can be assigned

multiple times as long as iCPD is not confirmed at the next assessment. PD in the non-target lesion category is confirmed if subsequent imaging, done four to eight weeks after iUPD, shows a further increase from iUPD.

The criteria for iCPD are not judged to have been met if RECIST 1.1 criteria for complete response or non-iCR/non-iUPD are met after a previous iUPD. The status is reset (unlike RECIST 1.1) and iCR, or non-iCR/non-iUPD is assigned; if no change is detected, the time point response is iUPD (Seymour, 2017). Changes in the largest diameter (unidimensional measurement) of the tumour lesions, but the shortest diameter of malignant lymph nodes are used in the RECIST v.1.1 criteria. In view of the potential for patients treated with immunotherapies to show early signs of disease progression, but ultimately to benefit from treatment, patients with evidence of progressive disease will also be evaluated using iRECIST criteria and may continue on study provided criteria outlined below are met.

RECIST 1.1 defines the appearance of new malignant lesions as denoting true disease progression, providing that other lesions (artefacts or benign intercurrent disease) are appropriately assessed and discounted if not malignant. If a new lesion is equivocal, for example because of its small size, continued therapy and follow-up assessment will clarify whether it represents truly new disease. If repeat scans confirm there is definitely a new lesion, then progression should be declared using the date of the initial scan (Eisenhaur, 2009).

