Aspects of new lesion assessment unique to iRECIST, include if a new lesion is identified (thus meeting the criteria for iUPD) and the patient is clinically stable, treatment should be continued. New lesions should be assessed and categorised as measurable or non-measurable using the RECIST 1.1 principles. a maximum of five lesions, no more than two per site, at least 10 mm in long axis (or 15 mm in short axis for nodal lesions), and recorded as New Lesions-Target (NLT) and New Lesion-Non-Target (NLNT) to allow clear differentiation from baseline target and non-target lesions. New lesions may either meet the criteria of NLT or NLNT to drive iUPD (or iCPD). However, the measurements of target lesions should not be included in the sum of measures of original target lesions identified at baseline. Rather, these measurements will be collected on a separate table in the case record form.

Results in UPD but iCPD is only assigned on the basis of this category if at next assessment additional new lesions appear or an increase in size of new lesions is seen ( $\geq 5$  mm for sum of new

lesion target or any increase in new lesion non-target). The appearance of new lesions when none have previously been recorded, can also confirm iCPD.

Other measurable and non-measurable lesions are recorded as new lesion non-target. New lesions do not need to meet the criteria for new lesion target to result in iUPD (or iCPD); new lesion non-target can also drive iUPD or iCPD. PD is confirmed (iCPD) in the new lesion category if the next imaging assessment, done at four to eight weeks after iUPD, confirms additional new lesions or a further increase in new lesion size from iUPD (sum of measures increase in new lesion target ≥5 mm, any increase for new lesion non-target in the absolute value of the sum of NLT or an increase (but not necessarily unequivocal increase) in the size of NLNT lesions or the appearance of additional new lesions.

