Note: Patients with a global deterioration of health status requiring discontinuation of treatment without objective evidence of disease progression at that time should be reported as "symptomatic deterioration." Every effort should be made to document the objective progression even after discontinuation of treatment.

**Table 6.** Evaluation of Best Overall Response for Patients with Non-Measurable Disease (i.e., Non-Target Disease).

Non-Target Lesions	New Lesions	Overall Response
CR	No	CR
Non-CR/non-PD	No	Non-CR/non-PD
Not all evaluated	No	not evaluated
Unequivocal PD	Yes or No	PD
Any	Yes	PD

\* 'Non-CR/non-PD' is preferred over 'stable disease' for non-target disease since SD is increasingly used as an endpoint for assessment of efficacy in some trials so to assign this category when no lesions can be measured is not advised

**Table 7.** Sequences of overall response assessments with corresponding best response.

1st Assessment	2nd Assessment	Best Response
IUPD	iCPD	PD
Stable, PR, CR	iUPD	Requires reassessment 4 - 8 weeks.
Stable	Stable	Stable
Stable	PR, CR	Stable
Stable	Not done	Not RECIST classifiable
PR	PR	PR
PR	CR	PR
PR, CR	Not done	Not RECIST classifiable
CR	CR	CR

Table 8. Overall Response for Patients with Neuroblastoma and Measurable Disease.

CT/MRI	MIBG	BM	Catecholamine	Overall
iUPD	Any	Any	Any	
Any	iUPD	Any	Any	PD
Any	Any	Any	Any	PD
Any	Any	iUPD	Any	PD
SD	CR/PR/SD	Non-PD	Any	SD
PR	CR/PR	Non-PD	Any	PR
CR/PR	PR	Non-PD	Any	PR
CR	CR	Non-PD	Elevated	PR
CR	CR	CR	Normal	CR

**Table 9.** Overall Response Evaluation for Neuroblastoma Patients and MIBG Positive Disease.

MIBG	CT/MRI	BM	Catechol	Overall
iUPD	Any	Any	Any	PD
Any	New Lesion	Any	Any	PD
Any	Any	Any	Any	PD
Any	Any	iUPD	Any	PD
SD	No New Lesion	Non-PD	Any	SD
PR	No New Lesion	Non-PD	Any	PR
CR	No New Lesion	Non-PD	Elevated	PR
CR	No New Lesion	CR	Normal	CR

• Only if patients are enrolled without disease measurable by CT/MRI, any new or newly identified lesion by CT/MRI that occurs during therapy would be considered progressive disease and not unconfirmed immune-progressive disease (iUPD) requiring reassessment to be diagnosed as iCPD.

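### Section 10.5 confirms progression of evaluable-only solid tumours by new-lesion findings alone, contrary to the protocol's own non-target rules

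*Protocol*

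**What the plan says.** Section 10.5 applies to solid tumours with evaluable disease, which it defines as "The presence of at least one lesion, with no lesion that can be accurately measured in at least one dimension". All baseline disease in these patients is therefore non-target.

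- **iUPD in 10.5** is triggered by "The appearance of one or more new lesions or evidence of laboratory, clinical, or radiographic progression". No new lesion is needed.
- **iCPD in 10.5** says only that "iUPD must be assessed between four to eight weeks to confirm progression and be deemed as iCPD". It gives no criterion.
- **PD in 10.5** repeats the iUPD trigger and then requires a next scan, taken within the four-to-eight-week window, that "confirms further progression from iUPD with either an increase of at least 5 mm in the absolute value of the sum of NLT". Its two alternatives are growth of NLNT, which need not be unequivocal, and further new lesions.
- **SD in 10.5** is whatever is not CR, PR or PD. The same section rules out PR for these patients.

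Section 10.2.5 makes clear that NLT and NLNT are categories of new lesion, "recorded as New Lesions-Target (NLT) and New Lesion-Non-Target (NLNT) to allow clear differentiation from baseline target and non-target lesions". For existing non-target disease it states: "PD in the non-target lesion category is confirmed if subsequent imaging, done four to eight weeks after iUPD, shows a further increase from iUPD". Table 6 (Section 10.7.1), for non-measurable disease, has columns for non-target lesions, new lesions and overall response. One of its rows reads "Unequivocal PD Yes or No PD".

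**The concern.** In evaluable-only patients the disease most likely to worsen is the disease already there, such as bone lesions, effusions or leptomeningeal spread. The PD entry written for them offers no way to confirm worsening of that disease, although the iUPD entry just above it lets such worsening start the process. The wording matches the PD paragraph of Section 10.4.2, which is labelled as dealing with new lesions. There it sits beside an iCPD entry with its own criterion and a note that makes substantial non-target worsening PD. In 10.5 the label, the criterion and the note are all absent.

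At stake are PFS, a secondary endpoint, and the SD count, which the synopsis says will be reported in the analysis of clinical benefit. Evaluable-only patients are eligible under criterion 5 of Section 4.2.2 and contribute to both.

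**Working it through.** The protocol gives no figure on this point, so the check sets the rules side by side for one test case. The patient has non-measurable disease at baseline and iUPD from growth of that disease. Four to eight weeks later there is further, unequivocal growth and no new lesion. The patient is clinically stable.

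1. **PD entry of 10.5.** Growth of NLT by 5 mm: not met, because there is no new lesion. Growth of NLNT: not met, for the same reason. Additional new lesions: not met. Result: not PD.
2. **SD entry of 10.5.** The case is not CR, not PR (unavailable) and not PD by step 1, so it falls into SD. The SD definition in 10.4.2 excludes an increase large enough for iUPD; the one in 10.5 does not.
3. **iCPD entry of 10.5.** Reassessment is required but no criterion is stated. Result: iCPD is possible but undetermined.
4. **Section 10.2.1.2.** Evaluable-only patients are assessed on whether their lesions are present, absent or progressing. Progression of existing lesions counts.
5. **Section 10.2.5.** Further increase from iUPD at four to eight weeks. Result: confirmed.
6. **Section 10.2.7.** Continued unequivocal non-target progression with more tumour burden is listed as confirming. Result: iCPD.
7. **Section 10.4.3.** Unequivocal progression of existing non-target lesions. Result: PD.
8. **Table 6.** Unequivocal non-target PD, new lesion or not. Result: PD.

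Steps 4 to 8 count the case as progression; steps 1 and 2 make it SD.

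**Effect on PFS.** The synopsis defines the event as disease progression or death and does not say whether the PD entry or iCPD of 10.5 supplies the progression.

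- If the PD entry is applied, the test patient has no event until a later qualifying new-lesion finding or death, so PFS is lengthened.
- If 10.2.5, 10.2.7 or Table 6 is applied, progression is recorded and this wording causes no bias.
- If the patient is clinically unstable, 10.2.7 uses the iUPD date, again with no bias from this wording.

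**Laboratory or clinical triggers.** 10.5 allows iUPD on this evidence, but its PD entry names only imaging for confirmation. Section 10.2.5 also speaks of imaging. How such an iUPD is confirmed is left open.

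**The case against.** The strongest reply is that the protocol as a whole does not leave these patients without a route to progression. The iCPD line in 10.5 carries no new-lesion limit, and 10.2.7 can be read into it. Section 10.4.1 also treats an iUPD, then a missed or non-evaluable scan, then another unconfirmed progression as iCPD. Section 10.2.7 keeps the label iUPD while its criteria are still met without worsening, so SD comes only from reading the residual definition in 10.5 by itself. Table 6 sits in the neuroblastoma part of Section 10, although its title covers non-measurable disease generally.

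Much of this stands, and it rules out several stronger readings that a reader might infer:

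- **That such a patient can never be classed as progressed.** This is true of the PD entry of 10.5 alone. Sections 10.2.5 and 10.2.7 would confirm the progression.
- **That PFS is overstated.** The documents support only a conditional risk: a clinically stable, evaluable-only patient who progresses in existing disease only, and a site or analyst who follows the PD entry.
- **That the other sections date the event at the first worsening.** Neither the non-target text of 10.2.5 nor Table 6 gives an event date. The dating sentence in 10.2.5 concerns equivocal new lesions.
- **That the protocol already has a rule for confirming laboratory or clinical progression.** It does not, and Section 10.3.5 says markers alone cannot be used to assess response.

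The reply does not remove the conflict. Section 10.5 is the section written for this population, and the only confirmation criteria it states are new-lesion ones. These are definitions that sites apply at each assessment. Central review under Section 8.3 reaches responders, pseudo-progression and SD of at least six cycles, so a shorter SD label rests on the local reading.

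**Conclusion.** The PD entry of 10.5 is wrong as written. It restricts confirmation to new-lesion findings and contradicts 10.2.1.2, 10.2.5, 10.2.7, 10.4.3 and Table 6. Taken literally with the residual SD definition, it labels growing existing disease as SD. The consequence is a possible excess of reported SD and a possible upward bias in PFS.

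The size cannot be computed, because neither the share of evaluable-only patients nor their progression pattern is given. It is limited to clinically stable patients with solid tumours and no measurable lesion who progress without a new lesion. CNS tumours, neuroblastoma, lymphoma and leukaemia have their own criteria, so this is a subset of the planned 50. The conclusion assumes that the PD entry is applied in preference to the other sections; where it is not, this wording produces no bias.

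**What to change.** Reconcile the PD and iCPD entries of 10.5 with 10.2.1.2, 10.2.5, 10.2.7, 10.4.3 and Table 6. One confirmation rule, covering existing non-target disease as well as new lesions, should then feed PD/iCPD and the PFS event. Exclude iUPD from the SD definition in 10.5, as 10.4.2 does. The sponsor should also reconcile how an iUPD triggered by laboratory or clinical evidence is confirmed, since 10.5 allows that trigger but names only imaging for confirmation. Confirmed progression also ends treatment (Sections 3.2 and 5.1), so the content of that rule is for the sponsor; the review asks only that the passages agree.

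The cost is a sentence or two. Aligning 10.5 with the existing imaging rule adds no assessments. Median PFS may come out slightly shorter.
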